9.3 Control Cohort Exclusion Criteria

At time of starting adjuvant (first-line) therapy:

- L. Prior treatment with anti-angiogenic agents including bevacizumab.
- M. Progressive disease (according to RANO criteria) after temozolomide/RT, at time of starting adjuvant therapy.
- N. Actively participating in another clinical treatment trial intended to treat the underlying astrocytoma at start of adjuvant Temozolomide treatment.

9.4 Control Cohort Lifestyle Considerations

- Patients enrolled in the control cohort must not have any past, present, or planned TT Fields treatment.

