2.1.2.3 The Optune Device

The Optune system (NovoTTF™ Therapy) is a portable battery- operated device, which produces TTFields within the human body by means of surface transducer arrays [45-47]. The TTFields are applied to the patient by means of surface transducer arrays that are electrically insulated, so that resistively coupled electric currents are not delivered to the patient. The transducer arrays, which incorporate a layer of adhesive hydrogel and a layer of hypoallergenic medical tape, are placed on the patient's shaved head. The transducer arrays must be replaced every three to four days and the scalp re-shaved in order to maintain optimal capacitative coupling between the transducer arrays and the patient head. All the treatment parameters are pre-set by Novocure so there are no electrical output adjustments available to the patient. Patients and their caregivers are instructed on proper procedures for changing and recharging depleted service batteries and connecting the device to an external battery pack overnight.

Optune is currently FDA-approved as a single modality treatment for recurrent GBM when both surgical and radiotherapy options have been exhausted. In the pivotal EF-11 trial in recurrent GBM, overall survival (OS) of patients treated with the device was equivalent to those treated with standard chemotherapy alone [46]. Six-month progression-free survival (6PFS) analysis favored the TTFields arm compared to the chemotherapy arm, although not statistically significant. Safety and toxicity profile favored the Optune arm compared to the chemotherapy control arm. No device-specific grade 3 and 4 toxicities were identified for hematologic, gastrointestinal, vascular, renal and respiratory disorders. There were also no increased grade 3 and 4 central nervous system adverse events. The most common device specific adverse event was skin rash due to the transducer arrays. In 2017, Optune was approved in combination with first-line adjuvant temozolomide for newly diagnosed GBM (see below).

2.1.2.4 Effect of Optune on Newly Diagnosed GBM Patients - A Phase 3 Study

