5.2 Exclusion Criteria

An individual who meets any of the following criteria will be excluded from participation in this study:

- A. Prior treatment with anti-angiogenic agents including bevacizumab.
- B. Prior treatment with TTFIELDS.
- C. Progressive disease (according to RANO criteria) after temozolomide/RT.
- D. Actively participating in another clinical treatment trial intended to treat the underlying astrocytoma.
- E. Females who are pregnant or breastfeeding.
- F. Significant co-morbidities at baseline (within 2 weeks prior to adjuvant temozolomide start) which would prevent adjuvant temozolomide treatment:
 - a. Thrombocytopenia (platelet count $< 100 \times 10^3/\mu\text{L}$)
 - b. Neutropenia (absolute neutrophil count $< 1.5 \times 10^3/\mu\text{L}$)
 - c. CTC grade 4 non-hematological toxicity (except for alopecia, nausea, vomiting)
 - d. Significant liver function impairment - AST or ALT > 5 times the upper limit of normal
 - e. Total bilirubin > 2 times upper limit of normal
 - f. Significant renal impairment (GFR ≤ 30 ml/min)
- G. Implanted pacemaker, programmable shunts, defibrillator, deep brain stimulator, other implanted electronic devices in the brain, or documented clinically significant arrhythmias.
- H. A skull defect such as missing bone with no replacement
- I. Bullet fragments embedded the skull
- J. Tumors located in the brain stem and/or the cerebellum.
- K. History of hypersensitivity reaction to temozolomide, Dacarbazine (DTIC) or hydrogel.

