9 CONTROL COHORT

This trial will include a control cohort that includes both historical and contemporaneous control patients. A minimum of 90 and a maximum of 100 patients will be enrolled in the control cohort. This is a non-interventional control group (data collection only). All patients in the control cohort will be enrolled at the same participating institutions. Risks associated with participation of the control cohort are minimal.

Historical controls will be gathered via chart review of patients completing chemo/RT after 1/1/2016 and before 5/20/2019; 5/20/2019 is the initial date of IRB approval for the coordinating center and first opened study site. Control patients completing chemo/RT after 5/20/2019 will be enrolled as contemporaneous controls.

Control subjects (contemporaneous or historical) will be enrolled via informed consent if consent is practicable. An IRB waiver of consent will be requested for historical control patients who may be deceased, no longer being followed or lost to follow-up.

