6. KPS
7. Summary of Adjuvant Chemotherapy (TMZ dates, number of cycles)
8. Summary of Additional Therapies (therapy types, dates, number of cycles)
9. Date(s) of Progression
10. Date of Death (if applicable)
11. Tumor tissue samples (optional)

Tumor Tissue samples are optional for control cohort patients. Adverse Events are not collected, and not reportable for control patients. MRI Correlative Study does not include control cohort participants. Concomitant Medications will not be maintained for control patients, although applicable steroid doses may be recorded as part of the RANO form.

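### The control rule on TTFields has no time point, so for chart-review controls eligibility can depend on treatment at recurrence, after Day 0

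*Combined protocol and SAP*

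**What the plan says.** Section 9.4 sets the rule for controls: "Patients enrolled in the control cohort must not have any past, present, or planned TT Fields treatment". The exclusions just before it, in section 9.3, sit under their own time point, "At time of starting adjuvant (first-line) therapy". That line heads the 9.3 list only and does not extend to 9.4.

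Section 9 describes how most controls are found: "Historical controls will be gathered via chart review of patients completing chemo/RT after 1/1/2016 and before 5/20/2019". It adds: "An IRB waiver of consent will be requested for historical control patients who may be deceased, no longer being followed or lost to follow-up". Section 10.1 expects 60 to 80 of the 90 controls to be historical.

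For the experimental arm, section 5.2 excludes "Prior treatment with TTFIELDS", which is judged at prospective enrolment.

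On availability at recurrence, section 2.1.2.3 says "Optune is currently FDA-approved as a single modality treatment for recurrent GBM", and section 2.1.1.1 says that these tumours are increasingly managed as molecular GBM. Section 9.5 already abstracts later treatment for controls: "Summary of Additional Therapies (therapy types, dates, number of cycles)". OS runs from Study Day 0 (Table 2) and is compared by log-rank test (section 10.2.1). The plan has no log of controls excluded for TTFields and no sensitivity analysis for that exclusion.

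**The concern.** When a chart is reviewed years later, past use means use at any time up to the review. A control who had standard first-line treatment and first received TTFields after progression is therefore ineligible, although nothing at Day 0 distinguished that patient from the others. The same exposure is judged at baseline in one arm and over the whole disease course in the other.

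To be removed in this way, a patient must live to progression and then long enough to start the device. If such patients tend to survive longer than the rest, removing them shortens control OS and makes TTFields look better with no treatment effect at all. The primary comparison is an unadjusted log-rank test (stratification is optional), so nothing in the analysis would correct this.

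**Working it through.** **1. Reproducing the plan's power figure.** Inputs from sections 10.1 and 10.2: control median 22 months, Weibull shape 2.0, 90 v 90, accrual 36 months plus 24 months of follow-up, control follow-up at most 60 months, one-sided alpha 0.05. For a 6-month gain:

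- Hazard ratio = (22/28)² = 0.617, so |ln HR| = 0.4823.
- Probability of death by time t with median m: 1 − 0.5^((t/m)²).
- Experimental follow-up uniform over 24 to 60 months: 67.6 expected deaths. Control follow-up uniform over 19 to 60 months: 74.2 expected deaths. The 19 is my assumption: a 60-month maximum less the 41-month window from 1/2016 to 5/2019. Total 141.8.
- Power = Φ(0.4823 × √(141.8/4) − 1.645) = Φ(2.872 − 1.645) = 0.890. Table 10 states 0.894.

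For gains of 4, 5, 7 and 8 months the same formula gives 0.644, 0.791, 0.948 and 0.977, against 0.649, 0.796, 0.950 and 0.979. The survival model is therefore the plan's own.

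**2. Effect of the exclusion with no treatment effect.** The documents give no rate of TTFields use at recurrence, so I let a share q of the controls who progress and live past a lag receive it, with no effect on survival. All users are removed from the control arm, and 90 v 90 are compared by one-sided log-rank test.

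- Model A: the protocol's OS (shape 2, median 22), median latent progression 4, 8 or 12 months, 2-month lag.
- Model B: OS is time to progression plus survival after progression, everyone progresses, 3-month lag.
- Model B+: as B, but 10% are long survivors who never progress, so can never be users and always stay in.

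| q | A: retained control median (22.0 if none removed) | A: error | B: error | B+: error |
|---|---|---|---|---|
| 10% | 21.7–21.9 | 0.059–0.070 | 0.05–0.07 | 0.040–0.053 |
| 30% | 21.0–21.4 | 0.084–0.115 | 0.06–0.11 | 0.025–0.046 |
| 50% | 20.0–20.6 | 0.13–0.23 | 0.10–0.22 | 0.009–0.045 |

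Under Model A the removed controls have a median OS of about 24 to 26 months. A further check used the same Weibull with progression at a random share of OS. With a 3-month lag and 9% to 28% of controls removed, error was about 0.06 to 0.08. With a 6-month lag it was about 0.13. With users kept it was 0.054, and across the other runs 0.046 to 0.055. Each Model B run had 1,500 replicates, so its simulation standard error is about √(0.05 × 0.95/1500) = 0.006. Differences at q = 10% are small against that.

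**3. How far B+ departs from the plan.** The protocol's Weibull gives 60-month survival of 0.5^((60/22)²) = 0.5^7.44 = 0.6%. B+ has more long survivors than that, but shows that the sign depends on who never progresses.

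**4. Price of keeping the users.** For a 6-month gain, power is about 0.88 with no users. If TTFields at recurrence has the full design hazard ratio of 0.617, power is about 0.85, 0.80 and 0.73 at 10%, 20% and 30% use. If its hazard ratio is 0.8, power is about 0.82 at 30% use.

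**The case against.** *The direction is assumed.* A reader might infer that the rule certainly removes longer-surviving controls and so favours TTFields. The documents do not support that. Patients who never progress cannot be users and stay in. With 10% long-surviving non-progressors the inflation disappears and usually reverses. Section 9.2 item G, read literally, requires adjuvant temozolomide to have been completed. That also conditions on the future and pushes the other way, although G.a asks only that it was given or planned. The net bias is therefore not established. This stands.

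*The size is assumed.* The approval at recurrence cited in section 2.1.2.3 is for GBM once surgery and radiotherapy are exhausted, and these controls are histologically Grade II or III. This shows availability in a related disease and gives no rate of use in this one. The larger error rates need high use or a long lag, neither of which is documented. This stands.

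*Not all controls are affected.* The 10 to 30 contemporaneous controls are judged at baseline if enrolled near adjuvant start. Those enrolled later are exposed: the group covers chemoradiation completed after 5/20/2019, but the cohort was added in the version of 16 December 2019. For historical controls a baseline reading is arguable, because section 10.1 says they would have met the trial's first-tier criteria. Section 9.4 does not say so.

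*A TTFields-free control arm is coherent.* The experimental regimen continues the device past first progression, so a comparison with no TTFields at any time is a legitimate question, and keeping users has a real cost in power. Granted. But removing patients because of later events does not answer that question without bias. Weighted censoring at the start of TTFields is the better route.

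**Conclusion.** The rule as written makes eligibility of chart-review controls depend on treatment after Day 0, and that holds whatever the sign of the bias. Under the protocol's own survival model, bias against the control arm is likely. One-sided error is about 0.06 to 0.07 if 10% of controls able to receive TTFields at recurrence did so, and about 0.08 to 0.13 if 30% did, although Model B goes as low as 0.05 and 0.06. These figures rest on assumed usage, an assumed lag and no long-surviving non-progressors. Neither a fixed size nor a certain net direction can be claimed. The change is worth making because it is cheap and removes the dependence altogether.

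**What to change.** - Reword section 9.4 so that the criterion applies at the start of adjuvant temozolomide: no prior, concurrent or planned first-line TTFields.
- Keep controls who first used TTFields after progression in the primary OS analysis.
- Count and report charts screened out for TTFields, with the reason and timing.
- Add a sensitivity analysis that censors controls at the start of TTFields with inverse-probability-of-censoring weights. Plain censoring would be informative, since users are likely to differ in prognosis. Therapy types and dates are already abstracted under section 9.5. Check that the covariates the weights need are abstracted too.

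The cost is one eligibility sentence, a screening log and one analysis. The statistical price is the dilution shown above, which is conservative and smaller if the effect at recurrence is weaker. At 30% use with the full design effect it takes power below the plan's 80%, so it should be stated alongside Table 10.

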9.5 Control Cohort Limited Data Collection

Data collected for the historical and contemporaneous control group will be distinct from data collected for interventional patients in this study, as described below. Data for control patients is designed to be collected exclusively from chart review.

All control cohort documentation should be uploaded into the eCRF within 45 days of collection. Data extracted from the medical record shall be defined as collected on the day of extraction.

1. Informed Consent or waiver
2. Demographics

3. Pathology
4. Date of and extent of operation (GTR, partial, or biopsy)
5. Summary of Concurrent Chemo/RT
6. KPS
7. Summary of Adjuvant Chemotherapy (TMZ dates, number of cycles)
8. Summary of Additional Therapies (therapy types, dates, number of cycles)
9. Date(s) of Progression
10. Date of Death (if applicable)
11. Tumor tissue samples (optional)

Tumor Tissue samples are optional for control cohort patients. Adverse Events are not collected, and not reportable for control patients. MRI Correlative Study does not include control cohort participants. Concomitant Medications will not be maintained for control patients, although applicable steroid doses may be recorded as part of the RANO form.

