1.3 Schedule of Activities (SoA)

TABLE 1: SCHEDULE OF ACTIVITIES: INTERVENTIONAL SUBJECTS

Study Procedure:	Screening ≤14 days prior to Day 0	Day 0 : Begin TMZ Treatment	Week 4 (-3/+7 days) and every 4 weeks until treatment stop	Week 8 (±7 days) and every 8 weeks only until treatment stop	Progression	After Treatment Stop (Week 4 (+/- 7 days) from end of treatment)	Survival follow-up
Informed Consent	X						
Medical History, Demographics	X						
Medication History	X						
MGMT methylation status	X						
Tumor Tissue Sample ⁹	X				X		
MRI of the brain ¹	X			X	X		
Physical Exam	X		X		X	X	
Neurological status, KPS	X		X		X	X	
CBC w/diff	X ¹⁰		X		X	X	
Pregnancy test (urine or serum)	X ¹⁰						
Biochemistry Panel ⁶	X ¹⁰		X		X	X	
Record Steroid Dose	X		X		X		
Quality of Life Questionnaires ²	X			X	X		
RANO	X			X	X		
Temozolomide Cycle		X ⁷	X ⁸				

Study Procedure:	Screening ≤14 days prior to Day 0	Day 0 : Begin TMZ Treatment	Week 4 (-3/+7 days) and every 4 weeks until treatment stop	Week 8 (±7 days) and every 8 weeks only until treatment stop	Progression	After Treatment Stop (Week 4 (+/- 7 days) from end of treatment)	Survival follow-up
Optune Therapy ⁴		X	X		X		
Optune Compliance ⁴			X				
Adverse Events		X	X	X	X	X	
Concomitant Medications		X	X	X	X	X	
Telephone Interview							X ⁵
DICOM Images shipped for electric fields mapping ¹¹		X			X		X

1) Screening MRI should be done within 21 days of study treatment start. MRI of the brain will be performed routinely at baseline and again every 8 weeks +/- 7 days until treatment termination or second progression, whichever is first. An MRI of the head will be obtained within 21 days in the event of clinical signs of progression. After the post-treatment follow up visit and the patient has not progressed by treatment termination, patient will have contrast-enhanced brain MRI every 3 +/- 1 months for 12 months, then every 6 +/- 2 months for 24 months, then yearly +/- 1 month thereafter or until disease progression, whichever comes first. All MRI scans should be performed with and without contrast and include the scalp.
							

2) Quality of Life will be measured using the EORTC QLQ-C30/BN20 and MMSE every 8 weeks +/- 7 days for the first 2 years then every 3 months thereafter.
							

3) Screening visit should occur within 14 days of adjuvant temozolomide start, with the exception of MRI which can be within 21 days (3 weeks) of adjuvant temozolomide start.
							

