6.1.1.2 Periodic Evaluation until Treatment Termination

Patients will be seen and examined before each cycle of temozolomide. After a maximum of 12 cycles of adjuvant temozolomide, patients will be seen every 8 weeks. Brain MRI and QoL assessments will be performed every 8 weeks following the baseline MRI for the first 2 years then every 3 months thereafter until second progression (when TTFIELDS treatment will be terminated).

Patients will undergo the following studies or review every month until treatment termination:

- Physical examination
- Neurological status and performance status (KPS)
- Blood exams
- Optune Compliance
- Record of Adverse Events, concomitant medications and steroid dose

Patients will undergo the following studies or review every 8 weeks +/- 7 days until treatment termination:

- Quality of Life Questionnaires (EORTC QLQ-C30/BN20, and MMSE)
- Contrast-enhanced MRI

Screening MRI should be done within 21 days of study treatment start. MRI of the brain will be performed routinely at baseline and again every 8 weeks +/- 7 days until treatment termination or second progression, whichever is first. In case of clinical progression, an MRI will be performed within 21 days.

All MRI scans should be performed with and without contrast.

The data collection for patients who remain on Optune (on-study treatment) and begin 2nd line therapy should include labs and visits adjusted as appropriate for the standard care of that patient's 2nd line therapy.

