The best overall response is the best response recorded from the start of the treatment until disease progression/recurrence (taking as reference for progressive disease the smallest measurements recorded since the treatment started). The patient's best response assignment will depend on the achievement of both measurement and confirmation criteria.

TABLE 5. SUMMARY OF THE RANO RESPONSE CRITERIA (ADAPTED FROM JCO 2010)

Criterion	CR	PR	SD	PD
T1 gadolinium enhancing disease	None	$\geq 50\%$ ↓	$< 50\%$ ↓ but $< 25\%$ ↑	$\geq 25\%$ ↑*
T2/FLAIR	Stable or ↓	Stable or ↓	Stable or ↓	↑*
New lesion	None	None	None	Present*
Corticosteroids	None	Stable or ↓	Stable or ↓	NA [†]
Clinical status	Stable or ↑	Stable or ↑	Stable or ↑	↓*
Requirement for response	All	All	All	Any*

Abbreviations: RANO, Response Assessment in Neuro-Oncology; CR, complete response; PR, partial response; SD, stable disease; PD, progressive disease; FLAIR, fluid-attenuated inversion recovery; NA, not applicable.

* Progression occurs when this criterion is present.

† Increase in corticosteroids alone will not be taken into account in determining progression in the absence of persistent clinical deterioration.

NOTE: Patients may continue on treatment and remain under close observation and evaluation at 4-8 week intervals if there is uncertainty regarding whether pseudoprogression may be present as determined by the investigators. If subsequent radiographic or clinical assessments suggest that the patient is in fact experiencing progression, then the date of progression should be the time point at which this issue was first raised. Similarly, stable disease may be assigned in cases of presumed “pseudoprogression” associated with decreased steroid use.

6.1.1.3.1.7 DURATION OF RESPONSE

Duration of overall response: The duration of overall response is measured from the time measurement criteria are met for CR or PR (whichever is first recorded) until the first date that recurrent or progressive disease is objectively documented (taking as reference for progressive disease the smallest measurements recorded since the treatment started).

The duration of overall CR is measured from the time measurement criteria are first met for CR until the first date that progressive disease is objectively documented.

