6.1.1.3.2 RESPONSE EVALUATION AFTER A COMPLETE RESECTION

A complete resection will be defined as contiguous contrast-enhancement <10 mm in 2 perpendicular measurements in each of 2 perpendicular planes (i.e., axial and coronal). Because neither the RECIST[80] nor MacDonald [81] criteria are completely appropriate for patients with minimal residual disease, a modified version of these criteria will be used as outlined below.

6.1.1.3.2.1 COMPLETE RESPONSE

Complete disappearance of enhancing tumor on consecutive CT or MRI images at least 1 month apart, and neurologically stable or improved and at the same or a lower steroid dose. To be assigned a status of “Complete Response” as a best overall response, changes in tumor measurements must be confirmed by repeat assessments that should be performed no less than 4 weeks after the criteria for response is first met.

6.1.1.3.2.2 PARTIAL RESPONSE

Partial response is not assessable in patients without sufficient measurable disease.

6.1.1.3.2.3 STABLE DISEASE

Insufficient change to qualify for Complete Response or Progressive disease.

6.1.1.3.2.4 PROGRESSIVE DISEASE

At least a 25% increase in the longest diameter on an axial image of any enhancing tumor on consecutive CT or MRI images with a minimum of ≥ 5 mm of contiguous contrast-enhancement in 2 perpendicular measurements in each of 2 perpendicular planes (i.e., axial and coronal).

6.1.1.3.2.5 NOT ASSESSABLE

Progression has not been documented and one or more sites have not been assessed.

6.1.1.3.2.6 POST-TREATMENT EVALUATION

After treatment termination the patient will be seen at an outpatient clinic for one additional visit within 30 days +/- 7 days. Physical and neurological examination, blood tests (CBC and Biochemistry panel) will be performed during this visit. Patient mortality and adverse events will be documented on the case report forms.

After the post treatment follow up visits, if the patient has not progressed by treatment termination, patient will have contrast-enhanced brain MRI every 3 +/- 1 months for 12 months. Then MRIs every 6 +/- 2 months for 24 months, then yearly +/- 1 month thereafter or until disease progression, whichever comes first.

In case of clinical progression an MRI will be performed within 21 days. After the end of study therapy visit post disease progression, the patient will not be required to return to the clinic for follow-up but will be followed until death by telephone every 3 months to monitor their status.

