10.2.1 Analysis of Primary and Secondary Endpoints and Correlative Studies

We will compare OS and progression-free survival (PFS) between historical control and experimental treatment arms using the log-rank test (we will also collect PFS data via chart review for the historical control patients). For our correlative studies, we will use the independent-sample t test to compare mean mutation burden between patient samples treated with RT+temozolomide or RT+temozolomide+TTFields. We may perform the same comparison within a linear regression framework if the need arises to adjust for any potential confounders for the effect of TTFields in our correlative studies.

To investigate the influence of electric field and energy deposition in the tumor on outcomes, we will use the Wilcoxon rank sum test to compare the electric field and specific absorption ratio parameters between: responders and non-responders; subjects with progression-free survival \geq and $<$ 1 year; subjects with overall survival \geq and $<$ 2 years; and subjects with overall survival \geq and $<$ 1.5 years. We will estimate Pearson correlation coefficients to assess the correlation of OS and PFS with electric field or specific absorption ratio parameters.

We may stratify the patients by MGMT methylation status, extent of resection, or a combination of the two.

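### PFS sets protocol-scheduled MRI in the TTFields arm against charted progression dates at unstated imaging intervals in controls, and Section 9.5 does not list the dates needed to check or correct for the difference

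*Combined protocol and SAP*

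**What the plan says.** **TTFields arm.** Footnote 1 of the Schedule of Activities (Section 1.3) states: "MRI of the brain will be performed routinely at baseline and again every 8 weeks +/- 7 days until treatment termination or second progression". Clinical signs of progression trigger an MRI within 21 days. Section 6.1.1.2 gives the long-run schedule as "every 8 weeks following the baseline MRI for the first 2 years then every 3 months thereafter". For patients who stop treatment without progression, Section 6.1.1.3.2.6 widens it: "patient will have contrast-enhanced brain MRI every 3 +/- 1 months for 12 months", then every 6 months for 24 months, then yearly. The note under Table 5 (Section 6.1.1.3.1.6) deals with uncertain pseudoprogression. If progression is later confirmed, "the date of progression should be the time point at which this issue was first raised".

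**Controls.** Section 9 makes the cohort non-interventional, and Section 9.5 adds: "Data for control patients is designed to be collected exclusively from chart review". The progression item on its data list is "Date(s) of Progression", followed by date of death. No control imaging interval appears anywhere. Section 9.5 mentions a RANO form in connection with steroid doses, and Section 11.2.2.1 requires a screening MRI report.

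**Analysis.** Section 10.2.1 compares PFS by the log-rank test and notes that "we will also collect PFS data via chart review for the historical control patients". It plans no interval-censored method, common assessment grid or sensitivity analysis for scan timing.

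**The concern.** Progression seen on imaging is not observed when it happens. It is recorded at the next scan, so the recorded time depends on how often the patient is scanned. When two arms are scanned at different intervals, an ordinary log-rank test on recorded dates picks up the difference in schedule as well as any difference in disease control.

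Here one arm has a protocol schedule, and the other follows whatever its sites did in routine care. PFS is a named secondary objective that contrasts exactly these groups. A shift from scan timing could hide part of a real PFS benefit or create an apparent one. The listed control items do not include the last progression-free MRI, which is needed to see how wide the uncertainty around each charted date is. They also give no date at which to censor a living control who has not progressed.

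**Working it through.** **1. The plan's own figure.** The plan gives no PFS median, effect size, event count or power, so the only figure to reproduce is OS power. Take the Table 10 cell with 90+0 controls, k = 2.0 and a 6-month gain.

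- HR = (22/28)² = 0.617, so ln HR = −0.482.
- Event probability at follow-up u is 1 − exp(−ln 2 · (u/median)²).
- TTFields: u uniform on 24 to 60 months, median 28, gives about 67.6 events of 90.
- Controls: entry spread over the 41 months from 1-2016 to 5-2019 with 60 months maximum, so u is uniform on 19 to 60, median 22, giving about 74.2 events of 90.
- Power = Φ(0.482/√(1/67.6 + 1/74.2) − 1.645) = Φ(1.22) = 0.889, against 0.894 stated.

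Death dates do not depend on scans, so nothing below changes this figure.

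**2. Direction of the effect.** Assume exponential true progression with median 4.0 months, the control figure of the phase 3 glioblastoma trial in Section 2.1.2.4. Then λ = ln 2/4.0 = 0.1733 per month and the true mean is 5.77 months. If each event is recorded at the next scan on a grid of width G, the mean recorded time is G/(1 − e^(−λG)):

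- 8 weeks (G = 1.84 months): 6.74 months
- 13 weeks (G = 2.99): 7.39 months
- 16 weeks (G = 3.68): 7.81 months

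With identical disease, 13-weekly controls appear to do better than 8-weekly TTFields patients by 7.39 − 6.74 = 0.65 months on average, and 16-weekly controls by 7.81 − 6.74 = 1.07 months.

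**3. Effect on the log-rank test.** Simulation with 90 per arm, TTFields scanned 8-weekly, ±1 week jitter and one-sided 0.05. The control intervals are assumptions. Equal true PFS, median 4.0 months:

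| Control interval | HR, all events scan-dated | Rejects for TTFields / for control | HR, 30% of events dated exactly |
|---|---|---|---|
| 4 weeks | 0.92 | 14% / 1.5% | 0.94 |
| 8 weeks | 1.00 | about 5% / 5% | 1.00 |
| 13 weeks | 1.11–1.13 | 1.1% / 20.5% | 1.08 |
| 16 weeks | 1.19–1.20 | 0.4% / 32% | 1.13 |

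Ranges are across repeated runs. Six-weekly control scans give HR 0.95 and a false-positive rate for TTFields of about 0.10, or about 0.07 with 30% dated exactly.

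The 30% column is an assumption that allows for deaths and clinical progression, which are not tied to a scan date.

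Longer medians shrink the effect. At 6.7 months with all events scan-dated, the HR is about 1.07 at 13 weeks and 1.11 at 16 weeks. At 10 months it is 1.03 to 1.07 for 12 to 16 weeks.

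**4. Effect on power.** With true HR 0.63 (the same phase 3 trial), control median 4.0 months and all events scan-dated, power is 92% with 8-weekly controls, 81% at 13 weeks, 67% at 16 weeks and 97% at 4 weeks. With 30% dated exactly, it is about 84% at 13 weeks and 75% at 16 weeks.

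**5. Does the remedy work?** An interval-censored Weibull proportional hazards model was fitted to null data with control intervals of 8, 13 and 16 weeks (600 runs per cell). It returns an HR of 0.997 to 1.010. Rejection is about 4–6% toward TTFields and 4.5–8% toward control. The highest rate came from a cell in which both arms were scanned 8-weekly, so it is not an effect of unequal schedules. The model needs the last progression-free scan date in both arms.

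**The case against.** The strongest reply is that the gap may be small or absent, and that several harsher readings go beyond the documents.

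- **A reader might infer that no control scan dates are collected.** The documents do not show that. A screening MRI report is required, and a RANO form is mentioned for controls. Section 11.2.2.1 says only that RANO forms are not needed at enrollment, so they may come later. The form's content is not given, so serial scan dates are unspecified rather than shown to be absent. If progression is charted at the detecting scan, that date is already held. The clear omissions are the last progression-free MRI and a last-assessment date.
- **A reader might infer that the bias can never be examined.** The charts are at the participating sites, and Section 11.1.7 makes REDCap the source-document repository. The dates can still be abstracted.
- **A reader might infer that TTFields progressions are routinely backdated.** The Table 5 note covers only uncertain pseudoprogression, and nothing excludes controls from it.
- **The TTFields schedule is not one fixed grid.** It widens after treatment stops, and Section 6.1.2.6 allows ±1 month for visits after temozolomide.
- **Scan-dating every event is a worst case.** Death counts as PFS failure (Section 6.1.1.3.1.9), and clinical deterioration can count as progression (Tables 3 and 4). The 4.0-month median comes from a glioblastoma trial whose control OS was 16 months, against 22 assumed here.
- **Sparser control scans work against TTFields.** In that case the risk is a missed benefit, not a false claim.

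These points limit the size and certainty of the concern. They do not remove it: the control interval is unstated, the list lacks the dates that would reveal it, and the planned test takes no account of it.

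**Conclusion.** The point holds as a design weakness of the secondary PFS comparison. Its size is unknown because the documents give no control imaging interval. That control imaging followed routine care is inferred from the non-interventional, chart-review design.

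Under the assumed intervals of 13 to 16 weeks and a 4.0-month median, equal true PFS appears as an HR of about 1.11 to 1.20 if all events are scan-dated. If 30% are dated exactly, it appears as about 1.08 to 1.13. Longer medians give less, and 8-weekly control scanning gives none. The direction follows the interval, so a reader should not conclude that the design favours TTFields, or that it disfavours it.

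Nor should the point be carried over to the primary endpoint: OS and the power in Table 10 do not depend on scan timing. No alpha or power is stated for PFS, so no stated PFS error rate is contradicted.

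**What to change.** 1. **Section 9.5, item 9.** For each control, also abstract the date of the last MRI without progression, the date and basis (MRI, clinical or histologic) of first progression, and the last assessment date if not progressed. If the RANO form already captures these, say so.
2. **Progression dating.** State that the pseudoprogression note under Table 5 applies to both arms.
3. **Section 10.2.1.** Prespecify an interval-censored PFS analysis in both arms, alongside the log-rank. Imaging progressions lie between the last progression-free MRI and the MRI first showing progression, deaths are dated exactly, and patients without progression are censored at their last assessment. Which of the two analyses leads is a matter of choice, but it should be fixed in advance.
4. **Reporting.** Tabulate observed scan intervals by arm, so that readers can see whether the schedules differed.

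The cost is a small amount of extra abstraction from charts already under review, and a slightly wider PFS confidence interval. Treatment, visits, imaging and sample size do not change.
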